7.1 Adverse Events

Adverse events will be collected, once the subject signs the ICF prior to undergoing Screening procedures, throughout the duration of the study. Treatment-emergent adverse events are those AEs starting after the subject receives the first dose of study drug. An AE is any unfavorable medical occurrence in a subject or clinical investigation subject administered a pharmaceutical product, which does not necessarily have to have a causal relationship with this treatment. An AE can therefore be any unfavorable and unintended sign, symptom, or disease temporally associated with the use of a medicinal (investigational) product, whether or not considered related to the medicinal (investigational) product. All AEs, including observed or suspected problems, complaints, or symptoms, are to be recorded on the appropriate eCRF. Documentation must be supported by an entry in the subject's source document. Each AE is to be evaluated for duration, severity, and causal relationship with the study drug or other factors.

Whenever possible, a specific disease or syndrome rather than individual associated signs and symptoms should be identified by the Investigator and recorded on the eCRF. However, if an observed or reported sign or symptom is not considered a component of a specific disease or syndrome by the Investigator, it should be recorded as a separate AE on the eCRF.

Any medical condition or signs or symptoms already present at Screening or Baseline should not be reported as an AE unless the medical condition or signs or symptoms present at Baseline worsen in severity or seriousness at any time during the study. In this case, it should be reported as an AE.

Clinically significant abnormal laboratory or other examination (e.g., ECG) findings that are detected during the study or are present at Baseline and significantly worsen during the study should be reported as AEs. The Investigator will exercise his or her medical and scientific judgment in deciding whether an abnormal laboratory finding or other abnormal assessment is clinically significant. Significant abnormal laboratory and other examination values occurring during the clinical study will be followed until repeat test results return to normal, stabilize, or are no longer clinically significant.

The ISRs observed during examination of injection sites by study staff should be recorded as AEs. The AE term “ISR” with grade of AE consistent with the worst grade for any 1 of the characteristics of the ISR (pain, swelling, erythema, etc.) should be reported.

ISRs observed by subjects will be reported in each subject’s eDiary and will not be recorded as AEs unless also observed by study staff.

Unexpected Adverse Drug Reaction

An unexpected adverse drug reaction is defined as an adverse reaction, the nature or severity of which is not consistent with the applicable product information (e.g., Investigator’s Brochure for an unapproved investigational product or package insert/summary of product characteristics for an approved product).

7.1.1 Grading and Intensity of Adverse Events

The Investigator will rate the intensity of each AE as mild, moderate, severe, or life threatening.

Severity or Toxicity Grading:

Grade 1: Mild – An event that is usually transient in nature and generally not interfering with normal activities.

Grade 2: Moderate – An event that is sufficiently discomforting to interfere with normal activities.

Grade 3: Severe – An event that is incapacitating with inability to work or perform normal daily activity.

7.1.2 Adverse Event Outcome

The Investigator will record the outcome of each adverse event as follows:

- Resolved
- Resolved with sequelae
- Not Resolved
- Death
- Unknown

7.1.3 Relationship to Study Drug

The assessment of the relationship of an AE to the administration of study drug (yes, no) is a clinical decision based on all available information at the time of the completion of the eCRF.

No (unrelated, not related, no relation, probably unrelated):

The time course between the administration of study drug and the occurrence or worsening of the AE rules out a causal relationship and another cause (concomitant drugs, therapies, complications, etc.) is suspected.

Yes (possibly related, related):

The time course between administration of study drug and the occurrence or worsening of the AE is consistent with a causal relationship and no other cause can be identified (concomitant drugs, therapies, complications, etc.).

The following factors should also be considered:

- Temporal sequence from drug administration;
Event should occur after study drug is given. The length of time from drug exposure to event should be evaluated in the clinical context of the event.
- Underlying, concomitant, intercurrent diseases;
Each report should be evaluated in the context of the natural history and course of the disease being treated and any other disease the subject may have.
- Concomitant medication;
Other drugs the subject is taking or the treatment the subject receives should be examined to determine whether any of them might be recognized to cause the event in question.
- Known response pattern for this class of drug;
Clinical and/or preclinical data may indicate whether a particular response is likely to be a class effect.
- Exposure to physical and/or mental stresses; and
Exposure to stress might induce adverse changes in the recipient and provide a logical and better explanation for the event.
- Pharmacology and PK of the test drug
Known properties (absorption, distribution, metabolism, and excretion) of the test drug should be considered.

Unexpected AEs – An unexpected AE is an experience not previously reported or an AE that occurs with specificity, severity, or frequency that is not consistent with the current Investigator's Brochure.

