7.1.6 Suspected Unexpected Serious Adverse Reactions

The Sponsor will send copies of expedited reports for all SAEs that are unexpected and suspected to be at least possibly related to the study treatment to all concerned regulatory authorities, active Investigator(s), and the IRBs/ECs in accordance with local and site-specific requirements. For all active Investigators located in Europe, the Sponsor or designee will be responsible for reporting suspected unexpected serious adverse reactions (SUSARs) and any other applicable SAEs to regulatory authorities including the European Medicines Agency (EMA), Investigators, and central or local ECs, as applicable, in accordance with national regulations in the countries where the study is conducted. SUSARs will be submitted within 7 days for fatal and life-threatening events and within 15 days for other serious events, unless otherwise required by national regulations.

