8.2.3 Safety Analysis

Safety data will be summarized and listed. No inferential statistical analyses of the safety data are planned. All safety summaries and listings will be generated using the Safety Population based upon treatment received for the Treatment Period of interest.

Safety data through Week 16 will be presented by the treatment received (CHS-1420 or Humira). Safety data for the study as a whole will be presented for subjects receiving CHS-1420 during Treatment Period 1 and those receiving

Humira during Treatment Period 1. Separate summaries will also be presented for Treatment Period 2 based upon the particular treatment sequence received in Treatment Periods 1 and 2: CHS-1420/CHS-1420, Humira/Humira and Humira/CHS-1420.

Safety data for the open label extension will be summarized separately. The primary focus of these summaries will be events that are recorded after beginning open-label treatment and events that began in Treatment Period 1 or 2 and worsen in severity in Treatment Period 3. The events will be summarized by treatment received in Treatment Period 2 and overall.

Adverse events will be coded and classified by system organ class and preferred term using the Medical Dictionary for Regulatory Activities (MedDRA). Data summaries will be based on TEAEs. All TEAEs will be listed and summarized by the subjects' treatment group (Treatment Period specific) when the events were reported. A summary of all drug-related AEs will also be generated. If there are any SAEs or any AEs leading to the discontinuation of study drug, a separate data listing will be generated.

Clinical laboratory data will be summarized descriptively and listed by treatment (Treatment Period specific) group. The change from pre-dose to the end of the study will also be summarized. For selected laboratory assessments, the frequency of abnormal values will be tabulated where abnormal ranges are available.

Prior and concomitant medications will be coded with the World Health Organization Drug Dictionary (WHO-DD) and listed. All concomitant medication taken after first dosing of study drug will be summarized.

Vital sign and ECG data will be summarized and listed by dose group and visit.

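### The yes/no causality definitions in 7.1.3 leave events with compatible timing and another identifiable cause in neither category, and conflict with their own labels and with 7.1.6

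*Combined protocol and SAP*

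**What the plan says.** Section 7.1.3 makes causality a binary rating by the investigator: "yes, no) is a clinical decision based on all available information". Each answer has a set of labels and a definition.

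- The labels for the negative answer are "No (unrelated, not related, no relation, probably unrelated". Its definition needs timing that "rules out a causal relationship and another cause (concomitant drugs, therapies, complications, etc.) is suspected".
- The labels for the positive answer are "Yes (possibly related, related". Its definition needs timing that "is consistent with a causal relationship and no other cause can be identified".

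The section then lists further factors to weigh: temporal sequence, underlying and intercurrent disease, other medication, known class effects, stress, and pharmacology. It gives no rule for an event that meets one condition of a definition but not the other.

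The rating is used or echoed in three other places:

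- Section 8.2.3, on the safety tables: "A summary of all drug-related AEs will also be generated".
- Section 7.1.4 (procedure for investigators): every SAE from Screening to 56 days after the last dose is reported whatever its cause. After that, reporting is required only for SAEs that the investigator rates as related.
- Section 7.1.6: expedited reports cover SAEs that are "unexpected and suspected to be at least possibly related to the study treatment".

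**The concern.** Both definitions join a timing condition and an alternative-cause condition with *and*, so neither is the complement of the other. The uncovered middle includes a foreseeable kind of event: one that follows dosing plausibly in a subject who also has another candidate explanation. The protocol's background (1.2) links psoriasis with diabetes, heart disease, arthritis and depression, and names infections and headache among the most common adverse events with adalimumab. The exclusion criteria remove uncontrolled diabetes only, and psoriatic arthritis is allowed. An infection in a subject with controlled diabetes is an example.

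At stake is whether the drug-related AE summary means the same thing at every one of approximately 160 sites (3.1), and whether a late SAE with a competing explanation is reported at all. Safety is part of the primary objective (section 2) and its analysis is descriptive only (8.2.3), so the drug-related table will be read at face value.

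**Working it through.** The plan states no figure on this point and no power or sample-size arithmetic applies. The check is a two-by-two table built from the two definitions in 7.1.3. It treats an identified and a suspected alternative cause as one condition, as the parallel wording of the definitions suggests.

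| Timing | Other cause | Meets *Yes*? | Meets *No*? | Result |
|---|---|---|---|---|
| Consistent | None | Yes | No | Related |
| Consistent | Present | No | No | **Undefined** |
| Ruled out | Present | No | Yes | Not related |
| Ruled out | None | No | No | **Undefined** |

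Two of the four combinations have no category. The last row matters little: if timing already rules causality out, any rater will answer *No*. The second row is the real gap.

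Labels against definitions:

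- *Yes* is labelled as including possible relationships, yet one identifiable alternative is enough to fail its definition. A possible relationship commonly has a competing explanation, so the definition is narrower than the label.
- *No* is labelled as including probably unrelated events, yet its definition requires timing that excludes causality altogether. An event with compatible timing that is probably due to something else has a label but no definition.

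Section 7.1.3 against 7.1.6: the expedited-reporting test is suspicion of at least a possible relationship. It has no condition that alternatives be absent. The only causality scale the protocol defines does not deliver that standard in the second row of the table.

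Where the rating has effect:

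| Output | Depends on the rating? |
|---|---|
| All TEAEs, listed and summarized (8.2.3) | No |
| SAE reporting up to day 56 after last dose (7.1.4) | No |
| Drug-related AE summary (8.2.3) | Yes |
| SAE reporting after day 56 (7.1.4) | Yes |
| Expedited reports up to day 56 (7.1.6) | Only if the sponsor uses the investigator's rating alone; not stated |

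The documents give no AE rates and no share of events with a competing cause, so the number of events in the undefined row cannot be computed.

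**The case against.** A reader might infer that drug-related AEs and SUSARs will be undercounted. The documents do not support that as a finding, for four reasons.

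- **Direction.** The events in the gap fail the literal *No* as well as the literal *Yes*. Downward bias arises if raters hold *Yes* strictly and relax *No*; the reverse choice gives upward bias. The possibly-related label may itself pull raters towards *Yes*.
- **Judgement.** The rating is described as a clinical decision, with further factors to weigh, including class effects. That weakens the view that a strict two-condition test governs. It does not close the gap: the factors carry no tie-break, and several of them send the rater looking for the very alternatives that defeat a literal *Yes*.
- **SUSARs.** Up to day 56, all SAEs reach safety personnel regardless of causality, and 7.1.6 states its own broader test for the sponsor. A loss of expedited reports in that window needs the added assumption that the sponsor relies only on the investigator's answer, and the protocol does not say so. After day 56 the dependence on the rating is direct.
- **Treatment comparison.** Treatment Periods 1 and 2 are double-blind, so misclassification has no evident reason to differ by arm. The primary endpoint is untouched.

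A reader might also take *Yes* to require that no other cause exists. The text asks only that none be identifiable, which is a lower bar. Nor does *Yes* exclude every possible relationship: compatible timing with no identified alternative can still be merely possible. These points limit the consequence. The incomplete definitions and the conflicts with the labels and with 7.1.6 stand.

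**Conclusion.** The point holds as a defect in a stated rule, not as a demonstrated undercount. One practically important combination has no category, and both definitions disagree with their own labels. The supportable consequence is inconsistent rating across sites, with under-classification as related where *Yes* is applied as written.

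Its reach is one descriptive safety summary and the reporting of SAEs after day 56, plus expedited reporting up to day 56 on the unstated condition that the sponsor relies solely on the investigator's rating. Total TEAE counts, and SAE counts up to day 56, do not depend on it. No between-arm bias is shown. The number of events affected is unknown. The conclusion rests on reading the two conditions in each definition as jointly required, which is what the text says. The wording should be corrected; the efficacy conclusions do not depend on it.

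**What to change.** Reconcile 7.1.3 with 7.1.6 so that the two answers are exhaustive and mutually exclusive:

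- *Yes*: a causal relationship with study drug is at least possible, whether or not another cause is identified.
- *No*: every other event.

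Keep the list of factors as guidance for deciding whether a relationship is possible, and repeat the two definitions in the eCRF guidance so that all sites apply the same rule. It would also help to state in 7.1.6 whose causality judgement triggers an expedited report, since the protocol leaves that open.

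The cost is a wording change in the protocol and the eCRF guidance. The downside is that somewhat more events will be classed as related.

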7.1.4 Serious Adverse Event Reporting

An SAE is any untoward medical occurrence that, at any dose:

- Results in death;
- Is life-threatening;

NOTE: An AE or adverse reaction is considered “life-threatening” if, in view of either the Investigator or Sponsor, its occurrence places the subject at immediate risk of death. It does not include an event that, had it occurred in a more severe form, might have caused death.

- Requires hospitalization or prolongation of an existing hospitalization;

NOTE: Any hospital admission with at least 1 overnight stay will be considered an inpatient hospitalization. An emergency room visit without hospital admission will not be recorded as an SAE under this criterion, nor will hospitalization for a procedure planned or scheduled before signing of the ICF. However, unexpected complications and/or prolongation of hospitalization that occur during elective surgery should be recorded as AEs and assessed for seriousness.

Admission to the hospital for social or situational reasons (i.e., no place to stay, live too far away to come for hospital visits) will not be considered inpatient hospitalizations.

- Results in a disability/incapacity;
- Is a congenital anomaly/birth defect; or
- Is an important medical event.

Note: Medical or scientific judgment should be exercised in deciding whether reporting is appropriate in other situations, such as important medical events that may not be immediately life-threatening or result in death or hospitalization but may jeopardize the subject or may require medical or surgical intervention to prevent 1 of the other outcomes listed in the above definition. These should also be considered serious. Examples of such events are invasive or malignant cancers, intensive treatment in an emergency room or at home for allergic bronchospasm, blood dyscrasias or convulsions that do not result in hospitalization, development of drug dependency, or drug abuse.

7.1.4 Serious Adverse Event Reporting—Procedure for Investigators

All SAEs occurring from Screening until 56 days (8 weeks) following the last administration of study drug must be reported to Worldwide Clinical Trials (WCT) Clinical Safety personnel within 24 hours of the knowledge of the occurrence. All SAEs occurring after the 56-day follow-up period, which the Investigator considers related to study drug, must also be reported to WCT Clinical Safety personnel.

To report the SAE, the Investigator is to complete the SAE form electronically in the electronic data capture (EDC) system for the study. When the form is completed, WCT Clinical Safety personnel will be notified electronically and will retrieve the form. If it is not possible to access the internet, a call should be made to the WCT SAE hotline (country specific phone numbers will be provided in the WCT Safety Plan and distributed to sites), and a completed paper SAE form should be faxed to WCT (fax number provided in the Study Manual) within 24 hours of awareness. When the EDC system becomes available, the SAE information must be entered within 24 hours of the system becoming available.

If the SAE is life-threatening or results in death, the Investigator is to telephone the Medical Monitor (telephone numbers are listed below).

The Investigator will be requested to supply detailed information regarding the event. All SAEs must also be reported to the reviewing IRB/EC according to IRB/EC policy, and a copy of that report must be retained at the investigative site and filed in the Investigator Site File in accordance with the requirements of that institution.

Safety Contact Information:

Worldwide Clinical Trials Clinical Safety
[name]
[name]
[name]
UK

Worldwide Clinical Trials SAE reporting – USA:

email: [contact]
[contact] (eFAX)

Worldwide Clinical Trials SAE reporting – Europe:

email: [contact]
[contact] (eFAX)

Specific contact information for Medical Monitors will be distributed to investigative sites in the contact numbers provided.

Country specific numbers will be provided to the Investigators.

7.1.5 Serious Adverse Event Follow-up

The Investigator must continue to follow the subject until the SAE has subsided or until the condition becomes chronic in nature or stabilizes (in the case of persistent impairment) or the subject dies.

Within 24 hours of receipt of follow-up information, the Investigator must update the SAE form electronically in the EDC system for the study and submit any supporting documentation (e.g., subject discharge summary or autopsy reports) to WCT Clinical Safety personnel via fax or e-mail. If it is not possible to access the EDC system, refer to the procedures outlined above for initial reporting of SAEs.

7.1.6 Suspected Unexpected Serious Adverse Reactions

The Sponsor will send copies of expedited reports for all SAEs that are unexpected and suspected to be at least possibly related to the study treatment to all concerned regulatory authorities, active Investigator(s), and the IRBs/ECs in accordance with local and site-specific requirements. For all active Investigators located in Europe, the Sponsor or designee will be responsible for reporting suspected unexpected serious adverse reactions (SUSARs) and any other applicable SAEs to regulatory authorities including the European Medicines Agency (EMA), Investigators, and central or local ECs, as applicable, in accordance with national regulations in the countries where the study is conducted. SUSARs will be submitted within 7 days for fatal and life-threatening events and within 15 days for other serious events, unless otherwise required by national regulations.

7.1.7 Breaking Study Blind for Regulatory Reporting

If a SUSAR is reported and, if required by local regulatory authorities, the Sponsor or designee will ascertain the treatment assignment by unblinding the subject for the purposes of regulatory reporting ONLY. The treatment assignment will only be known by necessary Sponsor employees/consultants or designees in Pharmacovigilance and Regulatory Affairs. (The subject and study site personnel are to remain blinded). The subject's status is unchanged and continued participation in the study is unaffected. If necessary to treat the AE or SAE for which the subject is being unblinded, the Investigator may be informed of the unblinded treatment assignment ([Section 4.6](#)).

7.2 Protocol Assessments

7.2.1 Physical Examination

A complete physical examination will be conducted by the Investigator or clinically trained designee (i.e., MD, NP) at Screening and will consist of general, head, eyes, ears, nose, throat, respiratory, gastrointestinal, extremity, musculoskeletal, cardiovascular, nervous system, lymph node, and dermatologic evaluations and height, weight, BSA, and any other physical conditions of note (e.g., percentage of BSA affected by chronic PsO, PASI score, and PSGA). Body mass index will be calculated. At all visits after Screening, abbreviated physical examinations will be performed and should include vital signs and evaluations of skin and joints and cardiovascular, respiratory, neurologic, and any other systems associated with the subject's complaints or AEs.

